#### 15.2.1 Primary outcomes

The dual primary outcomes are:

 Patient-reported quality of physical function scale recovery (using the EORTC-QLQ-C30) at 30 days after surgery

Surgical complications (using the CCI) score at 30 days after surgery

The primary outcome measures will be analysed using mixed effects GLM (General linear model) techniques to estimate the adjusted mean difference between groups and corresponding 97.5% confidence intervals

Supporting analysis based on the dual primary outcomes to assess differences between groups (F4S vs Usual Care) will use multivariate models, which will enable multiple outcomes to be analysed simultaneously, allowing for the correlation between them. Robust estimates will be generated, and type I error / family-wise error rate maintained at an acceptable level (5%).

### 15.2.2 Secondary outcomes

Continuous variables will be summarised using mean, standard deviation, median and range values as appropriate, and linear regression methods used to calculate an adjusted mean difference between groups along with a 99% confidence interval. Categorical data will be summarised using the number of patients, proportions, and log-binomial models used to obtain adjusted relative risks and 99% confidence intervals.

Repeated measures: Health / Mental health, Motivational processes, Physical Status/ exercise capacity: these numerical rating scores will be analysed using repeated measures techniques. The associated group differences will be calculated along with 99% confidence intervals.

## 15.2.3 Planned subgroup analyses

Subgroup analyses will be limited to the same variables as used in the minimisation algorithm (see section 6.2.3) and performed on the two primary outcomes only. The effects of these subgroups will be examined by including an intervention group by subgroup interaction parameter in the regression model, which will be presented alongside the effect estimate and 97.5% CI within subgroups. The results of subgroup analyses will be treated with caution and will be used for the purposes of hypothesis generation only.

### 15.2.4 Missing data and sensitivity analyses

Every attempt will be made to collect full follow-up data on all study participants; it is thus anticipated that missing data will be minimal. Participants with missing primary outcome data will not be included in the primary analysis in the first instance. This presents a risk of bias, and sensitivity analyses will be undertaken to assess the possible impact of the risk. In brief, this will include a multiple imputation approach where missing data not at random will be imputed using multivariate imputations by chained equations following the methods of White and colleagues [56]. Twenty imputation cycles will be used, as this has previously been demonstrated to produce adequate results [57,58].

A compiler average causal effect analysis (CACE) (only those patients who are compliant with treatment allocation) will be carried out to assess the effect in those who adhered to their randomised allocation [55].

The different elements of the intervention (Nutrition, Exercise and Health information) and use/access to rehabilitation services (eg. Maggies centres) will be analysed to assess the effect is consistent across the treatment group. This will be performed with the inclusion of an interaction term.

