## 15. STATISTICAL CONSIDERATIONS

# 15.1. Sample size

Sample size has been calculated based on the dual primary outcomes measure of:

- Patient-reported quality of physical function scale recovery (using the EORTC-QLQ-C30) at 30 days after surgery
- Surgical complications (using the CCI) score at 30 days after surgery

For the assessment of the physical function domain of the EORTC-QLQ-C30 using the method of Frison and Pocock for repeated measure design (one Baseline and one Post-Randomisation score), 320 participants in each group (640 in total) will provide 90% power

-----

at the 2.5% significance level (two-sided) to detect a 5 point difference (MCID), assuming a SD of 20, correlation of 0.6 and a 20% attrition rate. [53]

For the assessment of CCI score, previous studies have established that the minimum clinical important difference (MCID) is 5 points [51]. A total sample size of 902 (451 in each arm) will provide 90% power at 2.5% significance level (two-sided) to detect the MCID of 5 points in CCI score, considering that for the usual care mean and standard deviation (SD) at 30 days are 9.4 and 19.0, respectively and a 20% attrition rate. [52]

We will adopt the sample size associated with CCI score as it is considered dominant and requires a larger cohort of participants to detect a significant difference.

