# 15.2. Analysis of outcomes

A separate Statistical Analysis Plan (SAP) will be produced and will provide a more comprehensive description of the planned statistical analyses. A brief outline of these analyses is given below.

The primary comparison groups will be composed of those participants randomised to the F4S App and Usual Care versus those randomised to Usual Care alone. All analyses will be based on the modified intention to treat principle, i.e., participants will be analysed in the intervention group to which they were randomised irrespective of adherence to randomised group or other protocol deviations, will only include those who received surgery.

For all outcomes, appropriate summary statistics and differences between groups, e.g. mean differences, will be presented. Where possible intervention effects will be adjusted for the minimisation variables listed in Section 6.2.3, and baseline values (where available). Given the structure of the data, nesting of patients by centre, centre will be included in the model in the primary analysis.

For the dual primary outcomes, differences between groups will be presented alongside 97.5% confidence intervals and p-values from two-sided tests also provided. To maintain an overall 5% Type I error rate, each comparison will be tested at a significance level of 2.5% to account for the increase in the risk of type I error associated with making two key comparisons. Thus, statistical significance will be set to p<0.025 (two sided). All secondary outcomes will be presented with 99% confidence intervals and no p-values.

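### The only missing-data sensitivity analysis described is labelled as handling data missing not at random (MNAR), but it states no departure from missing at random (MAR), so it does not address MNAR

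*Protocol*

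**What the plan says.** Section 15.2.4 of the protocol sets the primary analysis as complete-case: "Participants with missing primary outcome data will not be included in the primary analysis in the first instance". It then states the consequence: "This presents a risk of bias, and sensitivity analyses will be undertaken to assess the possible impact of the risk". The one missing-data analysis it goes on to describe is "a multiple imputation approach where missing data not at random will be imputed using multivariate imputations by chained equations", and it adds that "Twenty imputation cycles will be used".

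No delta shift, pattern-mixture model, reference-based imputation or tipping-point analysis appears anywhere in the protocol. The other analyses in section 15.2.4 are a complier average causal effect analysis and interaction analyses of the intervention elements. Both concern adherence or consistency of effect, not missing outcomes.

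On the expected amount of missing data, section 15.2.4 says "it is thus anticipated that missing data will be minimal". Section 15.1 sizes the physical function outcome with a "correlation of 0.6 and a 20% attrition rate", and sizes the Comprehensive Complication Index (CCI) with the same 20% loss.

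**The concern.** The sentence names one missingness mechanism and a method that assumes another. Chained-equations imputation draws each missing value from a model fitted to observed values. Without an explicit departure term, it supposes that missing patients resemble observed patients with the same recorded characteristics. An MNAR mechanism is precisely one in which they do not.

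If the sentence is followed as written, the trial report could present a MAR imputation as an MNAR check. Agreement between it and the complete-case result would then be read as reassurance on a question that was not examined.

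The point has force in this trial for three reasons:

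- Participants and clinical teams know the allocation (section 6.3).
- One of the two primary outcomes is self-reported.
- The day-30 questionnaires are completed in clinic (section 12.3), so patients who are recovering poorly may be the ones who do not attend or do not complete them. This last step is an inference; the protocol gives no data on it.

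**Working it through.** **Step 1. The loss fraction in the plan.** Inputs from section 15.1: two-sided alpha 0.025 (z = 2.241), power 90% (z = 1.282), difference 5, SD 19 for CCI, SD 20 and correlation 0.6 for physical function, 20% attrition. The formula is n per arm = 2 × (2.241 + 1.282)² × SD² / 5².

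- CCI: 2 × 12.41 × 361 / 25 gives 359; 359 / 0.80 gives 449 per arm, 898 in total. The plan states 902.
- Physical function: baseline-adjusted SD = 20 × √(1 − 0.6²) = 16. Then 2 × 12.41 × 256 / 25 gives 255; 255 / 0.80 gives 319 per arm. The plan states 320.

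Both figures reproduce, so 20% is the loss that the plan itself allows for. It is used below as the upper case, with 5% as an assumed low case.

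**Step 2. What a departure does to the estimate.** Let m be the missing fraction in an arm and d the amount by which that arm's missing values differ from what MAR predicts. The bias in the treatment difference is (m × d) in one arm minus (m × d) in the other. With a departure in one arm only, it is m × d:

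| Departure d (assumed) | 20% missing | 5% missing |
|---|---|---|
| 5 points | 1.0 | 0.25 |
| 10 points | 2.0 | 0.5 |
| 15 points | 3.0 | 0.75 |

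The MCID is 5 points for both outcomes. Equal departures with equal missingness in both arms cancel (0.20 × 10 − 0.20 × 10 = 0). A common departure of 10 with 25% and 15% missing gives 0.10 × 10 = 1.0 point.

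**Step 3. Whether MAR imputation would reveal it.** Simulation of 300 trials for physical function: 451 per arm, SD 20, correlation 0.6, 20 imputations by arm given baseline. Assumed missingness is 20% at random under usual care, and 20% in the app arm with the log-odds of being missing rising by 1 for each 20-point lower score. Mean estimates:

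| Analysis | True difference 0 | True difference 5 |
|---|---|---|
| Full data | 0.03 | 5.05 |
| Complete case | 2.21 | 7.34 |
| MAR imputation | 2.27 | 7.39 |
| Delta-adjusted (−13 in missing app-arm values) | −0.33 | 4.80 |

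MAR imputation returned almost the same biased answer as the complete-case analysis. The delta shift moved it by 0.20 × 13 = 2.6 points (2.27 − 2.6 = −0.33), as the formula predicts. The simulated bias of 2.27 − 0.03 = 2.24 points corresponds to a departure of 2.24 / 0.20 = 11.2 points, inside the range in step 2.

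**Step 4. Scale.** With 451 × 0.80 ≈ 361 completers per arm, the standard error for physical function is 16 × √(2/361) = 1.19 and the 97.5% CI half-width is 2.241 × 1.19 = 2.67. At 20% missing, a one-arm departure of 2.67 / 0.20 ≈ 13 points moves the estimate by one half-width; at 5% missing it takes 2.67 / 0.05 ≈ 53 points.

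**The case against.** The strongest reply is that this is a protocol summary. The list of sensitivity analyses is introduced with "In brief, this will include a multiple imputation approach", so it is not exhaustive, and section 15.2 says "A separate Statistical Analysis Plan (SAP) will be produced and will provide a more comprehensive description of the planned statistical analyses". That SAP is not at hand and may contain an MNAR analysis. A reader might infer that the complete-case result is never tested; the documents do not support that. MAR imputation that uses recorded information, such as day-14 scores, does test the part of the bias that observed data explain. Only the MNAR part is untouched. Nor can one say that chained equations are incapable of handling MNAR: imputed values can be shifted. The protocol simply states no shift. This reply limits the point but does not remove it, because the mismatch is in the protocol's own sentence and an SAP that follows it inherits the mislabel.

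The complier analysis does not fill the gap. Section 7.8 makes completion of the 30-day questionnaires part of adherence in both arms, so those without them are non-adherent by definition.

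The magnitudes are also open to challenge, and fairly. The departures are assumed and placed in one arm. The 20% is a planning allowance; because section 15.2 restricts the analysis to those who had surgery, cancelled operations may account for part of it. The simulation imputed from baseline alone, so useful auxiliary variables would recover some of the bias. CCI is assessed at discharge and day 30 alongside routine note review (sections 9 and 10), so its missingness need not follow that of the questionnaires.

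Other stronger readings do not stand:

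- Non-return of a postal form is not the mechanism, since section 12.3 has the day-30 booklet completed in clinic with staff checks.
- The reference to twenty cycles is loose wording; the title of reference 57, cited there, concerns the number of imputations.
- An expectation of minimal missing data can coexist with a 20% allowance.
- The protocol does not say that physical function will be imputed after death, and that rule is commonly left to the SAP.
- A baseline-adjusted day-30 analysis is legitimate; a repeated-measures primary model would be a preference.

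**Conclusion.** The point holds in a limited form. Section 15.2.4 attaches an MNAR label to a method for which it states no departure from MAR. The only missing-data sensitivity analysis it describes therefore leaves MNAR unaddressed and could seem to corroborate a biased complete-case estimate. This is an error in what the protocol states, not an absent detail. It affects a sensitivity analysis and not the sample size or the primary model.

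The possible bias ranges from negligible to material: 0.25 to 0.75 points at 5% missing and 1 to 3 points at 20% missing, against an MCID of 5. These figures assume a departure of 5 to 15 points in one arm only. They illustrate what could go unseen and do not predict what will happen.

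**What to change.** Amend section 15.2.4, and carry the change into the SAP before any unblinded results are seen:

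1. Describe the multiple imputation as performed under MAR, with 20 imputed datasets, and name auxiliary variables already collected. For physical function these could be the day-14 and 3-month scores; for CCI, the complications recorded at discharge.
2. Add a separate MNAR analysis for both primary outcomes, either delta-adjusted imputation or a tipping-point analysis. Vary the departure independently by arm, including departures in one arm only, over a range fixed in advance. For physical function, 0 to 15 points in the unfavourable direction would cover the illustration above; the trial team should justify the range for CCI.
3. Report the departure at which the conclusion at the 2.5% level would change, next to the observed missing fraction in each arm.

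The cost is a few lines of text and modest extra programming. No new data, no additional participants and no change to the primary model are needed.

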#### 7.4. Intervention Modification or Cessation

The F4S App will not be available to participants who are randomised to the usual care arm of the trial, so crossover will not be possible from usual care. It is possible that participants randomised to the F4S arm will cease to engage with the App completely. This will not however be considered a crossover, since this is part of the pragmatic nature of the trial.

As mentioned in section 7.3 the App is designed to adapt to the participant as they use it, or cease to use it. The variability in engagement with the App forms part of the trial and will be captured by the App.

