#### 7.8. Adherence

Adherence to the intervention arm will be defined as using the app at least twice a week in the time before surgery and the completion of quality of life questionnaires 30 days after surgery.

Adherence to usual care will be the completion quality of life questionnaires 30 days after surgery.

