## 8. OUTCOME MEASURES

#### 8.1. Internal Pilot Outcome

The success of the 6-month internal pilot study will be based upon the recruitment rate (overall and at individual sites), completeness of primary outcome data (quality of life questionnaires 30 days after surgery in each arm of the study) and adherence to the intervention (adherence in the intervention arm will be defined as using the App at least twice a week in the time before surgery).

We will recruit 125 participants (14% of the total sample) during the 6-month internal pilot phase. We will open 2 sites in the first month, then 3 sites a month for the next 5 months until a maximum of 17 sites are open in the pilot phase.

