# 8.2.2 Secondary Outcomes

\* Adherence defined as per section 7.8 Adherence.

- Days Alive and at Home Within 30 days (DAH30)
- Patient-reported quality of life (using the EORTC-QLQ-C30 & LC 29) at 14 days, 30 days, 3 and 6 months after surgery
- Mental health/well-being (using the Hospital Anxiety and Depression Scale (HADS))
- Symptom score (using a 0-10 point VAS) (intervention only)
- Motivational processes
- Physical status assessed by the incremental shuttle walk test (ISWT), sit to stand test and hand grip test
- Patient-generated subjective global assessment short form (PG-SGA SF)

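### The CACE sensitivity analysis is described as a compliers-only comparison, and the adherence definition it would rely on removes App non-users from one arm only and conflicts with Section 8.1

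*Protocol*

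**What the plan says.** Section 15.2.4 lists, among the sensitivity analyses: "A compiler average causal effect analysis (CACE) (only those patients who are compliant with treatment allocation) will be carried out". Its stated aim is the effect among those who adhered to their allocation, and it cites a CACE primer (reference 55). It does not say which adherence definition applies.

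Section 7.8 is the only place that defines adherence for both arms. For F4S it requires "using the app at least twice a week in the time before surgery and the completion of quality of life questionnaires 30 days after surgery". For the comparator: "Adherence to usual care will be the completion quality of life questionnaires 30 days after surgery".

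Section 8.1 gives a different rule for the pilot: "adherence in the intervention arm will be defined as using the App at least twice a week in the time before surgery". The footnote to Table 1 then points the other way: "Adherence defined as per section 7.8 Adherence".

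Section 7.4 explains that usual-care participants have no access to the App, "so crossover will not be possible from usual care". Section 15.2 sets the main analysis as modified intention to treat among those who had surgery, regardless of adherence.

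**The concern.** A CACE keeps every participant in the randomised arm and uses allocation as the instrument to recover the effect in those who would comply. Keeping only compliers in each arm is a per-protocol contrast. It loses the protection of randomisation, whatever it is called.

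With the Section 7.8 definitions the selection differs by arm. F4S participants must have used the App enough and returned the day-30 form. Usual-care participants need only return the form. People who would not have used the App therefore leave one arm and stay in the other. If they are frailer or less motivated, the contrast could favour F4S with no treatment effect, and it would be reported under a causal label.

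The questionnaire element raises a second issue for the CCI. Complications are assessed at discharge and at day 30 (Section 9), with note review (Section 10), so a CCI score can exist without the form. Such participants would be dropped. Anyone who dies before completing the form is necessarily among them, and death is Grade V in Appendix I.

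**Working it through.** **1. Design figures reproduced (Section 15.1).** Per-arm n = 2(z₀.₉₈₇₅ + z₀.₉₀)² SD²/δ², with (2.241 + 1.282)² = 12.41.
- CCI: SD 19, δ 5 gives 359 per arm; 359/0.8 = 449; total 898 against 902 stated.
- Physical function: SD 20 × √(1 − 0.6²) = 16, δ 5 gives 255 per arm; 255/0.8 = 319; total 638 against 640 stated.

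Both agree closely with the stated figures. The point below does not depend on them, except that 5 points is the yardstick for the bias.

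**2. Who would be compared.** Inputs: 451 per arm and 20% attrition (15.1); App adherence p from 0.5 to 0.8, spanning the Modify band to the Go threshold in Table 1. Assume questionnaire return is independent of App use.
- Usual care: 451 × 0.8 ≈ 361.
- F4S: 361 × p ≈ 180 (p = 0.5), 235 (p = 0.65), 289 (p = 0.8).

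**3. Bias of the compliers-only contrast.** Let μ_C and μ_N be the untreated means in would-be App adherers and non-adherers, with g = μ_C − μ_N. With no treatment effect:
- F4S adherers have mean μ_C.
- Usual-care responders have mean p μ_C + (1 − p) μ_N = μ_C − (1 − p) g.
- The difference is (1 − p) × g.

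The protocol gives no value for g, so 0, 5 and 10 points on physical function are assumed. Spurious difference, in points:

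| p | g = 0 | g = 5 | g = 10 |
|---|---|---|---|
| 0.5 | 0 | 2.5 | 5.0 |
| 0.65 | 0 | 1.75 | 3.5 |
| 0.8 | 0 | 1.0 | 2.0 |

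A simulation with 2 million participants per scenario (SD 20, 80% response independent of App use) matches these to within 0.1. With a true complier effect of 5, the rule returns 5 + (1 − p) × g, that is 5 to 10 points.

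Section 15.2 plans adjustment for minimisation variables and baseline values where available, so g should be read as the gap left after adjustment. The same formula holds for the CCI with its own gap and the sign reversed, since lower is better.

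**4. The standard estimator under the same assumptions.** Because control participants cannot receive the App, non-compliance is one-sided and CACE = ITT difference / p. In the same simulations this stayed between −0.02 and 0.09 when the true effect was 0, and between 4.97 and 5.07 when it was 5.

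**5. The questionnaire requirement, outcome by outcome.**
- Physical function: without the day-30 form there is no outcome, and Section 15.2.4 already leaves such participants out of the primary analysis in the first instance. The requirement adds nothing.
- CCI: participants with a known score are lost, deaths before the form necessarily among them.

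**6. Sections 7.8 and 8.1 side by side.** Section 8.1 uses App use alone. Section 7.8 adds questionnaire completion, which Table 1 already scores in its own row. If App use and completion were each 80% and independent, adherence would be 80% under 8.1 (Go) but 0.8 × 0.8 = 64% under 7.8 (Modify).

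**The case against.** The best defence is that a CACE is by definition an effect in compliers, so the parenthesis may only name the target population. The sentence uses the right term and cites a primer on the method. Section 15.2 calls itself a brief outline, and the choice of estimator can properly be left to the SAP. This has some force, but the words limit the analysis to compliant patients, and a questionnaire-based definition of usual-care adherence serves no purpose in a true CACE with one-sided non-compliance. Anyone who follows the text literally would run a per-protocol comparison.

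It is also true that Section 15.2.4 does not cite Section 7.8. The link is an inference, made because no other definition covers both arms.

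Several stronger readings are tempting but unsupported:
- *That the questionnaire rule itself tilts the comparison towards F4S.* It applies to both arms. If return depends on the same factors in each, it changes the population without creating a difference between arms. The asymmetry comes from App use.
- *That all seriously ill patients would be excluded.* Day-30 forms are completed in clinic with staff help where needed (Section 12.3). Only deaths before completion are lost by necessity.
- *That the analysis must favour F4S.* With g = 0 there is no App-use bias, and a gap in the other direction would reverse it.

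**Conclusion.** The concern holds for the CACE sensitivity analysis as worded. It describes a compliers-only comparison and, if Section 7.8 governs, breaks randomisation by selecting on App use in one arm only. The bias is (1 − p) × g: 0 to 5 points on physical function under no effect, for assumed p of 0.5 to 0.8 and g of 0 to 10. It matches the 5-point target difference only in the most extreme of these cases (p = 0.5, g = 10). These are ranges, not estimates, because the protocol supplies neither quantity. For the CCI there is also a loss of participants with known scores, which the documents do not allow to be sized.

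The conflict between Sections 7.8 and 8.1 stands however 15.2.4 is read. A reader might infer that the trial's main conclusion is at risk. It is not: the primary analysis is modified intention to treat, and neither the significance level nor the sample size is touched.

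**What to change.** - **Section 15.2.4:** replace the parenthesis with wording such as: all participants in the modified intention-to-treat population are kept in their randomised arm; the CACE is estimated with allocation as the instrument; receipt means App use twice weekly or more before surgery, and is zero in usual care.
- **Section 7.8:** remove questionnaire completion from the adherence definition so that it agrees with Section 8.1. The Table 1 footnote can then stay as it is.
- **Missing questionnaires:** handle them as missing outcome data under the multiple imputation already planned, not as non-adherence.
- **Companion analysis:** repeat the CACE with a lower or graded usage threshold.

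The cost is mainly wording, since App usage data already go to the trials unit (Table 3). There are two statistical costs. The interval will be wider than for the per-protocol contrast. The estimate also relies on the exclusion restriction: participants below the threshold may still benefit from the exercise, nutrition or information components, before or after surgery (Section 7.3). Dividing by p would then credit their benefit to the adherers and could inflate the CACE, which is why the companion analysis is needed.

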#### 7.1. Usual Care

This may be a range of healthcare services that provides all or one of the following: information for the participants (with or without links to further information), formal rehabilitation via physiotherapy, dietician support via dietician, and/or routine follow up as per standard of care.

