# 7.2. F4S App and Usual Care

This will combine the usual care interventions as per section 7.1 and use of the F4S App (for a minimum of 2 weeks prior to surgery) with details described in the following sections.

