## 7.3. F4S App

The advice given to the participant is determined by their unique, dynamic, personal health status. That is, as a participant engages with the App, the advice regarding exercise and nutrition adapts.

Specifically, the App collects baseline demographic data, comorbidities, symptom burden using simple questions and Visual Analogue Scales (VAS), and the outcome measures of Quality of Life, Health and wellbeing scores. This information is used to deliver personalised feedback, support and guidance when using the App. e.g. if diabetic, guidance on avoiding a hypoglycaemic event. This will not constitute trial data and is part of the data to inform the intervention itself.

The digital programme or 'App' comprises three prehabilitation interventions:

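### The planned interaction for intervention elements and rehabilitation-service use is either not estimable or conditions on post-randomisation behaviour, so it cannot show whether the effect is consistent

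*Protocol*

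**What the plan says.** Section 15.2.4 (missing data and sensitivity analyses) states that "The different elements of the intervention (Nutrition, Exercise and Health information) and use/access to rehabilitation services" "will be analysed to assess the effect is consistent across the treatment group". On method it adds: "This will be performed with the inclusion of an interaction term". It does not say how an element is coded or what it interacts with.

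Other sections bear on this:

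- Section 7.3: the App "comprises three prehabilitation interventions", namely exercise, nutrition and health information. Section 6.2.3 randomises individuals 1:1 to the whole package plus usual care or to usual care alone; the components are not randomised separately.
- Section 7.4: "The F4S App will not be available to participants who are randomised to the usual care arm of the trial".
- Section 7.1: usual care may itself include "information for the participants (with or without links to further information), formal rehabilitation via physiotherapy, dietician support via dietician". Section 7.2, on the F4S arm, says: "This will combine the usual care interventions as per section 7.1 and use of the F4S App".
- Section 9 and Table 2: the questions on usual care and the record of nutritional input (drinks and dietitian) are scheduled in both arms on the day of surgery and at 30 days. Neither is scheduled at baseline.
- Section 6.3: clinical teams and participants know the allocation.
- Section 15.2.3: subgroup analyses are confined to the minimisation variables and are for hypothesis generation only.

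**The concern.** A test of whether a treatment effect is consistent needs a modifier that exists in both arms and that allocation cannot influence. The modifiers named here fail one condition or the other.

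The App's components fail the first, because the control arm has none of them. Care received from any source and individual service use fail the second. They are recorded weeks after an open allocation, and the App, which offers exercise, nutrition and advice, could itself change how much other help a participant seeks. The day-30 record also overlaps the period in which both primary outcomes develop, so complications may drive service use rather than the reverse.

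At stake is interpretation. The analysis would yield either a term that the software drops or a contrast between self-selected groups presented as evidence on consistency. It sits under sensitivity analyses, so it also lacks the hypothesis-generation caveat that Section 15.2.3 attaches to subgroup results.

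**Working it through.** **The plan's own figure, for context only.** Section 15.1 gives 902 participants for the CCI (difference 5, SD 19.0, two-sided 2.5%, 90% power, 20% attrition). Per arm, n = 2 × (19/5)² × (2.2414 + 1.2816)² = 28.88 × 12.41 = 358.4, so 359. Then 359/0.8 = 448.75, so 449 per arm and 898 in total. A t-based calculation gives 360, and 360/0.8 = 450 per arm. Both agree with 902 to within 3%. Nothing here disputes that figure; 451 × 0.8 = 360.8, or 361 analysed per arm, is used below only as a realistic scale.

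**Model.** Let A be arm (1 = F4S) and E the element. An interaction model is Y = b0 + b1·A + b2·E + b3·A·E, and the consistency question concerns b3.

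**Reading 1: E is use of an App component.** By Section 7.4, E = 0 whenever A = 0. Only three distinct rows (1, A, E, A·E) can occur:

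- usual care: (1, 0, 0, 0)
- F4S, not used: (1, 1, 0, 0)
- F4S, used: (1, 1, 1, 1)

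The last two columns are identical, so the rank is 3 of 4. Only b2 + b3 can be estimated, and that is users minus non-users within F4S. If every F4S participant is coded as having the element, then E = A·E = A and the rank is 2 of 4. A numerical check at 361 per arm gave the same ranks. Fitting an interaction within F4S alone avoids the aliasing, but it has no randomised comparator and compares self-selected uptake.

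**Reading 2: E is care from any source, or individual use of rehabilitation services.** Section 7.1 allows counterparts of all three elements in usual care, so all four cells can be filled. With 10%, 30% or 50% of usual-care participants assumed to receive the element, the rank was 4 of 4 and the model can be fitted. What b3 estimates is

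b3 = (users − non-users in F4S) − (users − non-users in usual care).

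Suppose the true effect is the same in everyone, the outcome depends on frailty with slope k per SD, and g1 and g0 are the mean frailty gaps between users and non-users in F4S and usual care. Then b3 = k × (g1 − g0), which is zero only if selection into use is the same in both arms.

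**Illustration (assumed values, not from the protocol).** Constant effect -5, SD 19, frailty–outcome correlation 0.4, so k = 19 × 0.4 = 7.6 points. The log-odds of use change by +0.7 per SD of frailty in usual care and by -0.7 in F4S. Over 2,000 simulated trials of 361 per arm:

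- the mean spurious interaction was -9.67 points;
- the hypothesis of no interaction was rejected at 2.5% in 87.5% of trials.

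Working back, g1 − g0 = -9.67/7.6 = -1.27, about 0.64 SD in opposite directions in the two arms. The range under the same inputs follows:

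| Selection into use | Spurious interaction |
|---|---|
| Opposite in the two arms | -9.7 |
| In F4S only | about -4.8 (half) |
| Equal and same direction in both | 0 |

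For scale, Section 15.1 takes 5 points as the minimum clinically important difference on the CCI.

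**The case against.** The best reply is that the plan names no model. Section 15.2.4 mentions only an interaction term, Section 15.2 calls itself an outline, and coding is ordinary material for the statistical analysis plan. That stands as far as coding goes. But the protocol already fixes the modifiers, the question and the method, and no coding of component uptake or individual service use makes them fit together.

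A reader might infer that the interaction cannot be fitted at all because the elements exist only in F4S. The documents do not support that. Section 7.1 lets usual care include information, physiotherapy and dietician support, and Table 2 records usual care and nutritional input in both arms. Non-estimability belongs to the App's own components; for the rest the fault is post-randomisation conditioning.

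A reader might also infer that the result would decide which parts of the App are kept. The protocol nowhere says so.

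It can be said, too, that a sound version exists. Section 7.3.2 tiers nutrition by PG-SGA score and Section 7.3.1 sets the suggested exercise level from a sit-to-stand test; both measures are scheduled at baseline in both arms. That is right and is taken up in the fix, but it is not the analysis that Section 15.2.4 describes. Likewise, access to services could be a site-level fact known in advance, but no such record is scheduled.

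Finally, the simulation assumes opposite selection in the two arms. That is fair: it shows that false inconsistency can arise, not how large it would be here.

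**Conclusion.** The point holds in a bounded form. For App components, the arm-by-element interaction is not identified at any sample size; this follows from Sections 6.2.3, 7.3 and 7.4 without further assumption. For care from any source and for individual service use, the model can be fitted, but it conditions on behaviour recorded only after open allocation and cannot show that the randomised effect is consistent. How far it would mislead depends on how selection into use differs between arms, which the documents do not tell us: from 0 to about 9.7 CCI points under the assumptions shown.

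The analysis is supplementary. The primary analysis, the error rate for the dual primary outcomes and the sample size are untouched. It should be corrected before analysis, but it does not threaten the trial's main conclusion.

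**What to change.** 1. In Section 15.2.4, remove the interaction on element uptake and on individual service use. Report uptake of each element descriptively within F4S, and use of rehabilitation services descriptively by arm.
2. If consistency is to be tested, name only modifiers fixed before allocation: for example, site-level rehabilitation provision recorded at site opening, or baseline PG-SGA SF or sit-to-stand category. Label these tests exploratory. The baseline list in Section 9 names randomisation ahead of the nutritional and physical assessments, so state that any such measure is taken before allocation.
3. Amend Section 15.2.3, which at present limits subgroups to the minimisation variables, so that the two sections agree and the hypothesis-generation caveat covers both.
4. Take any adherence-related effect from a complier average causal effect analysis that keeps the randomised comparison. Section 15.2.4 currently glosses that analysis as restricted to compliant patients, so it cannot be relied on as worded.

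The cost is protocol and analysis-plan wording, plus one item on the site set-up form if site provision is used. The trial would claim no component-specific effect, but a design that randomises the package as a whole cannot supply one.
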